15.0 Drug Information

Patients will be treated according to companion treatment protocol or clinical standard of care.

16.0 Statistical Considerations and Methodology

16.1 Overview

This is a screening protocol that is designed to identify patients with actionable genomic alterations and recommend them to an appropriate companion trial. A patient who has an actionable genomic profile is defined as a patient with one or more actionable alteration where the patient qualifies to be screened for a COLOMATE companion trial based on the information recorded on the COLOMATE companion trial recommendation form.

16.2 Primary Endpoints

There are two primary endpoints for this trial:

- The first primary endpoint is "actionable genomic profile" defined as a patient who
 received a trial recommendation per the COLOMATE companion trial
 recommendation form.
- The second primary endpoint is "companion trial enrollment" defined as a patient who has an actionable genomic profile that enrolls in their recommended companion trial.

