- 7.32 Actionable alteration is defined as a genomic alteration/mutation profile that qualifies a patient to be screened for one companion trial.
- 7.4 Patients for whom 1 actionable alteration is identified

If an actionable alteration is identified, the treating physician will be notified of any available COLOMATE companion trials on the COLOMATE Companion Trial Recommendation Form.

- 7.41 Patients who choose to enroll in a COLOMATE companion trial and meet eligibility criteria will be treated according to that companion trial protocol.
- 7.42 Patients who decline participation on the COLOMATE companion trial or do not meet eligibility criteria can subsequently register with COLOMATE ≥60 days after previous registration for a maximum of 3 times or at the discretion of the Study Chair.
- 7.5 Patients for whom ≥ 2 actionable alterations are identified

If more than one actionable alteration is identified, COLOMATE companion trial recommendations will be prioritized according to the following algorithm: 1) fusions; 2) amplifications; 3) all other alterations. If the algorithm does not assign a patient to one companion clinical trial, the report will be referred to the COLOMATE PI and/or a COLOMATE steering committee designee and statistician for adjudication.

- 7.51 Patients who choose to enroll in a COLOMATE companion trial and meet eligibility criteria will be treated according to that companion trial protocol.
- 7.52 Patients who decline participation on a COLOMATE companion trial or do not meet eligibility criteria can re-register with COLOMATE ≥60 days after previous registration for maximum of 3 times or at the discretion of the Study Chair.
- 7.6 Patients for whom no actionable alteration is identified

If no actionable alteration is identified, the treating physician will be notified of any other COLOMATE companion trials for which the patient may be eligible on the COLOMATE Companion Trial Recommendation Form. The patient can re-register with COLOMATE ≥60 days after previous registration for maximum of 3 times or at the discretion of the Study Chair.

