16.4 Sample Size

The total sample size of COLOMATE will be approximately 500 patients. The sample size for each individual companion trial will depend on the prevalence of the actionable genomic alterations and availability of companion trials.

For ACCRU-GI-1611, there is no formal hypothesis testing.

Given 500 patients, assume X% of patients can be assigned to a companion trial, the corresponding 95% confidence interval is shown in the table below. The sample size of 500 allows us to have good precision (i.e. confidence interval width less than 10%) in estimating the proportion of patients recommended into a companion trial.

Assumed proportion of patients can be recommended to a companion trial $(X\%)$	Confidence interval
10%	(7.37%, 12.63%)
20%	(14.49%, 23.51%)

30%	(25.98%, 34.02%)
40%	(35.71%, 44.29%)
50%	(45.62%, 54.38%)
60%	(55.71%, 64.29%)

Assume 40% of the patients will be recommended to a companion trial (i.e. N=200) and further assume X% of patients would enrolled into the recommended trial, the corresponding 95% confidence interval is shown in the table below. With a sample size of 500 and 40% of patients recommended, we also have decent precision (i.e. confidence interval width less than 15%) in estimating the proportion of patients enrolled into the recommended trials among those recommended. Given the fact that ACCRU-GI-1611 is actively opening additional companion trials, we do not expect less than 40% of patients will be recommended to a companion trial.

Proportion of patients enrolled into the recommended companion trial (X%)	Confidence interval
5%	(1.98%, 8.02%)
10%	(5.84%, 14.16%)
15%	(10.05%, 19.95%)
20%	(14.46%, 25.54%)
25%	(19.00%, 31.00%)
30%	(23.65%, 36.35%)

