16.5 Analysis Plan

16.51 Primary Endpoints

For the analysis of the first primary endpoint, the proportion of patients who
have an actionable genomic profile will be calculated. This is defined as the
total number of eligible patients who have an actionable genomic profile
divided by the total number of eligible patients whose genomic profile is
available for COLOMATE steering committee review.

A patient may come back to ACCRU-GI-1611 for subsequent screening (see sections 7.5, 7.5, and 7.6); therefore, a patient can contribute information to the first primary endpoint more than once.

- Our goal is to have at least 20% of patients have actionable genomic profile. The endpoint will be presented as a point estimate along with a 95% confidence interval (by Wald asymptotic confidence limit).
- For the analysis of the second primary endpoint, the proportion of patients that enroll in the companion trial recommended by the COLOMATE committee will be calculated. This is defined as the total number of eligible patients that enroll in the recommended companion trial divided by the total number of eligible patients who have an actionable genomic profile.

A patient may come back to ACCRU-GI-1611 for subsequent screening (see sections 7.4, 7.5, and 7.6); therefore a patient can contribute information to

the second primary endpoint more than once.

• Our goal is to enroll at least 75% of patients who have an actionable genomic profile. The endpoint will be presented as a point estimate along with a 95% confidence interval (by Wald asymptotic confidence limit).

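### The first primary endpoint has two definitions: Section 16.1 requires an actionable alteration, while Section 16.2 requires only a trial recommendation on the form, which could take in Section 7.6 patients who have none

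*Combined protocol and SAP*

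**What the plan says.** Section 16.1 defines a patient with an actionable genomic profile as "a patient with one or more actionable alteration where the patient qualifies to be screened for a COLOMATE companion trial", judged from the Companion Trial Recommendation Form. Section 7.32 also ties the word actionable to the genomic result: "Actionable alteration is defined as a genomic alteration/mutation profile that qualifies a patient to be screened for one companion trial".

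Section 16.2 takes the same term as the first primary endpoint and defines it again, as a patient who "received a trial recommendation per the COLOMATE companion trial" recommendation form. It does not mention an alteration. The second primary endpoint is "a patient who has an actionable genomic profile that enrolls in their recommended companion trial".

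Section 16.51 uses the "total number of eligible patients who have an actionable genomic profile" as the numerator of endpoint 1 and the denominator of endpoint 2. It sets goals of at least 20% and at least 75%, and does not say which definition applies.

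Section 7.6 covers patients with no actionable alteration. For them, "the treating physician will be notified of any other COLOMATE companion trials for which the patient may be eligible", and this is done on the Companion Trial Recommendation Form. Section 7.4, for patients who do have an alteration, uses the same verb and the same form: "the treating physician will be notified of any available COLOMATE companion trials".

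**The concern.** A primary endpoint should classify each patient in one way only. Here a patient without an actionable alteration, but with another companion trial listed under 7.6, fails the 16.1 definition and can meet the 16.2 definition. The text does not say whether a 7.6 listing is a recommendation.

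If such patients count, endpoint 1 no longer measures the yield of blood-based profiling alone. It also reflects how many companion trials happen to be open that need no alteration. Endpoint 2 changes as well, because the same patients enter its denominator and, if they enrol, its numerator. The study is descriptive, so the reported proportions are its results, and they will be read against the 20% and 75% goals.

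**Working it through.** **Comparing the definitions.**

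| Patient | Meets 16.1? | Meets 16.2 read literally? |
|---|---|---|
| Actionable alteration, trial recommended (7.4, 7.5) | Yes | Yes |
| No actionable alteration, other trial listed on the form (7.6) | No | Possibly |
| No actionable alteration, no trial listed | No | No |

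Only the second row is in dispute. The verb does not settle it, since 7.4 and 7.6 both speak of notifying the physician. Section 7.31 describes the completed form as carrying trial recommendations and does not limit that to patients with an alteration. Section 16.4 plans in terms of patients recommended, and argues that because "ACCRU-GI-1611 is actively opening additional companion trials, we do not expect less than 40% of patients will be recommended to a companion trial". That fits either reading.

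**The plan's own figure.** Section 16.51 names the Wald interval, p ± 1.96 × √(p(1−p)/n). For the planning case in 16.4, p = 0.40 and n = 500: √(0.24/500) = 0.02191, half-width 0.0429, interval 35.71% to 44.29%, as printed. The 20% row in that table prints a lower limit of 14.49%; the formula gives 16.49%, which is used below. That looks like a misprint and has no bearing on this point.

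**Endpoint 1.** Let p be the share with an actionable alteration and q the share of the remaining patients given a 7.6 listing.

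- Under 16.1: p
- Under 16.2 read literally: p + (1 − p)q

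Inputs: n = 500 is the sample size in 16.4, taken here as 500 patients with a reviewable profile. The documents give no q. They give p only for EGFR-refractory disease (30–40%, Section 1.1). Every p and q below is therefore an assumption.

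| Case | Under 16.1 (Wald 95% CI) | q | Under 16.2 (Wald 95% CI) |
|---|---|---|---|
| a. Any p | p | 0 | p (no difference) |
| b. p = 15% | 75/500 = 15.0% (11.9–18.1) | 25/425 = 5.9% | 100/500 = 20.0% (16.5–23.5) |
| c. p = 20% | 100/500 = 20.0% (16.5–23.5) | 100/400 = 25% | 200/500 = 40.0% (35.7–44.3) |
| d. p = 30% | 150/500 = 30.0% (26.0–34.0) | 50/350 = 14.3% | 200/500 = 40.0% (35.7–44.3) |

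In case b the 20% goal is missed under one definition and met under the other. In cases c and d it is met under both, but the estimate moves by 20 and 10 percentage points.

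**Endpoint 2, in case c.** Suppose 75 of the 100 patients with an alteration enrol: 75/100 = 75.0%. Adding the 100 patients with a 7.6 listing makes the denominator 200.

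| 7.6 patients who enrol | Endpoint 2 under 16.2 |
|---|---|
| 0 | 75/200 = 37.5% |
| 20 | 95/200 = 47.5% |
| 75 | 150/200 = 75.0% |
| 100 | 175/200 = 87.5% |

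Endpoint 2 can move either way. It falls whenever 7.6 patients enrol less often than patients with an alteration.

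**The case against.** The two sections can be harmonised. Section 16.1 opens by describing the protocol as finding patients with actionable alterations and recommending them to trials, so recommending already attaches to alterations. Section 16.2 reuses the defined term and cites the same form, and may be shorthand. Section 7.6 speaks of trials for which a patient may be eligible, which is weaker than qualifying for screening. Section 7.32 is broad: any mutation profile that opens a companion trial is already actionable. The disputed group is then limited to patients listed for trials that their profile does not open, and the documents name no such trial. The form itself is not in the documents and may already separate the two kinds of listing. The only case that crosses a goal takes p at half the lower end of the 30–40% range. Finally, a recommendation-based endpoint could be deliberate, since 16.4 is worded that way.

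Much of this stands. The alteration-based reading is probably what was meant, the disputed group may be small or empty, and the scenarios illustrate rather than estimate. But the harmonised reading is not forced. Section 16.2 is worded as a definition in its own right and omits the alteration, and 7.6 expressly foresees companion trials for patients without one. No sentence excludes those listings from the endpoint.

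**Conclusion.** The concern holds. One term carries two definitions in adjacent sections, and the protocol itself creates the patients on whom they can differ. Both primary endpoints depend on which definition is used, although endpoint 2 is internally consistent once one is chosen.

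The size cannot be taken from the documents. It is zero if no 7.6 listings occur or if they are not treated as recommendations. Under the assumed values above, endpoint 1 rises by 5 to 20 percentage points, and endpoint 2 could lie anywhere from 37.5% to 87.5% instead of 75.0%, the extremes being that none or all of the 7.6 patients enrol. Section 16.3 makes all analyses descriptive, so no test or error rate is affected, and 16.51 attaches no decision rule to the goals. The point should be settled before analysis, so that the definition is not chosen with the results in view.

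**What to change.** - **Section 16.2:** define the first primary endpoint as at least one actionable alteration per 7.32 together with a companion-trial recommendation based on that alteration. This follows 16.1, 7.32 and the goal in 2.11 of molecularly assigned therapy.
- **Section 16.51:** state that this set of patients is the numerator of endpoint 1 and the denominator of endpoint 2, and that 7.6 listings count in neither.
- **Recommendation form:** if it does not already do so, record for each listed trial whether it is matched to an alteration (7.4, 7.5) or is a 7.6 listing.
- **Reporting:** give 7.6 listings and any enrolments from them on a separate descriptive line, so no information is lost.

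The cost is one sentence in each of the two sections and at most one form field. Section 18.1 already collects the Guardant360 results and the recommendation form, so patients already registered can be classified. The trade-off is that the reported actionable proportion may be lower. If the sponsor does intend the recommendation-based endpoint, 16.1 and 16.51 must say so, and the endpoint needs a name that does not imply an alteration.

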16.3 Statistical Design

This is a screening protocol and is not designed to test a specific hypothesis. All analyses will be done in descriptive fashion only.

16.4 Sample Size

The total sample size of COLOMATE will be approximately 500 patients. The sample size for each individual companion trial will depend on the prevalence of the actionable genomic alterations and availability of companion trials.

For ACCRU-GI-1611, there is no formal hypothesis testing.

Given 500 patients, assume X% of patients can be assigned to a companion trial, the corresponding 95% confidence interval is shown in the table below. The sample size of 500 allows us to have good precision (i.e. confidence interval width less than 10%) in estimating the proportion of patients recommended into a companion trial.

Assumed proportion of patients can be recommended to a companion trial $(X\%)$	Confidence interval
10%	(7.37%, 12.63%)
20%	(14.49%, 23.51%)

30%	(25.98%, 34.02%)
40%	(35.71%, 44.29%)
50%	(45.62%, 54.38%)
60%	(55.71%, 64.29%)

Assume 40% of the patients will be recommended to a companion trial (i.e. N=200) and further assume X% of patients would enrolled into the recommended trial, the corresponding 95% confidence interval is shown in the table below. With a sample size of 500 and 40% of patients recommended, we also have decent precision (i.e. confidence interval width less than 15%) in estimating the proportion of patients enrolled into the recommended trials among those recommended. Given the fact that ACCRU-GI-1611 is actively opening additional companion trials, we do not expect less than 40% of patients will be recommended to a companion trial.

Proportion of patients enrolled into the recommended companion trial (X%)	Confidence interval
5%	(1.98%, 8.02%)
10%	(5.84%, 14.16%)
15%	(10.05%, 19.95%)
20%	(14.46%, 25.54%)
25%	(19.00%, 31.00%)
30%	(23.65%, 36.35%)

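### Section 16.4, first precision table: the lower confidence limit in the 20% row should be 16.49%, not 14.49%

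*Combined protocol and SAP*

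**What the plan says.** Section 16.4 states that there is no formal hypothesis test and justifies about 500 patients by precision. The first table, for 500 patients, is introduced with "assume X% of patients can be assigned to a companion trial, the corresponding 95% confidence interval is shown in the table below". Its 20% row prints 14.49% to 23.51%. From this table the section concludes: "The sample size of 500 allows us to have good precision (i.e. confidence interval width less than 10" percentage points). A second table, for 200 patients, covers the second primary endpoint.

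Section 16.51 sets the target for the first primary endpoint: "Our goal is to have at least 20% of patients have actionable genomic profile". It specifies that the estimate will be reported with a 95% interval "by Wald asymptotic confidence limit". Section 16.4 does not itself name the interval method.

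**The concern.** A Wald interval is symmetric about the estimate. The printed 20% interval has its midpoint at 19%, so at least one of its limits must be wrong if the table uses the method of Section 16.51. The row also breaks the pattern of the table: at a fixed sample size a Wald interval is widest at 50%, yet the printed 20% row is wider than the 50% row.

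What is at stake is the stated precision at the plan's own goal. A reader of the printed row would think that an observed 20% in 500 patients leaves a true 15% inside the interval. The plan's method puts 15% outside it.

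**Working it through.** **Inputs.** n = 500 and a 95% level (Section 16.4); Wald method (Section 16.51), so z = 1.96; p = 20% (the row in question, and the goal in Section 16.51).

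**Formula.** p ± z × sqrt(p(1 − p)/n).

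**Does this formula reproduce the table?** With n = 500:

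| Assumed p | Computed | Printed | Printed midpoint | Printed width (points) |
|---|---|---|---|---|
| 10% | 7.37% to 12.63% | 7.37% to 12.63% | 10% | 5.26 |
| 20% | **16.49%** to 23.51% | **14.49%** to 23.51% | **19%** | **9.02** |
| 30% | 25.98% to 34.02% | 25.98% to 34.02% | 30% | 8.04 |
| 40% | 35.71% to 44.29% | 35.71% to 44.29% | 40% | 8.58 |
| 50% | 45.62% to 54.38% | 45.62% to 54.38% | 50% | 8.76 |
| 60% | 55.71% to 64.29% | 55.71% to 64.29% | 60% | 8.58 |

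All six rows of the second table (n = 200) also reproduce to two decimals. Eleven of the twelve rows therefore confirm that the tables use the Wald formula.

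**The 20% row.**
- Standard error: sqrt(0.20 × 0.80 / 500) = sqrt(0.00032) = 0.01789.
- Half-width: 1.96 × 0.01789 = 0.03506, or 3.51 points.
- Limits: 20 − 3.51 = 16.49% and 20 + 3.51 = 23.51%.
- Error in the printed lower limit: 16.49 − 14.49 = 2.00 points.
- Width: 2 × 3.506 = 7.01 points, against 23.51 − 14.49 = 9.02 printed. The ratio is 9.02 / 7.01 = 1.29, so the printed interval is 29% too wide.
- Upper bound on width at n = 500: 2 × 1.96 × sqrt(0.25 / 500) = 8.77 points, reached at p = 50%. The printed 9.02 exceeds it, so no 95% Wald interval at n = 500 can have that width.

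**Could another method or sample size explain 14.49%?** For 100 of 500 at 95%:
- Wilson: 16.73% to 23.73%
- Clopper-Pearson: 16.58% to 23.78%
- Agresti-Coull: 16.72% to 23.74%
- Jeffreys: 16.67% to 23.67%
- Continuity-corrected Wald: 16.39% to 23.61%

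A 99% Wald interval gives 15.39% to 24.61%. None has a lower limit of 14.49%. Taken separately, the printed lower limit implies n = 0.16 × (1.96 / 0.0551)² ≈ 202 and the printed upper limit implies n = 0.16 × (1.96 / 0.0351)² ≈ 499, so no single sample size yields both.

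**Is it a row carried over from the second table?** No. The 20% row there is 14.46% to 25.54%. It is correct for n = 200 and differs from the printed row in both limits.

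**The case against.** The strongest reply is that nothing in the plan depends on this row, and most of that reply stands.

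- **The precision claim survives.** Printed and correct widths are both under 10 points. The correct 50% row, the worst case for width, establishes the claim for every proportion.
- **No decision uses the limit.** Section 16.3 makes the analyses descriptive, the 20% goal is not tied to a confidence limit, and the reported interval will come from observed data.
- **The 20% row is not the expected result.** Section 16.4 expects no less than 40% of patients to be recommended to a companion trial, and the 40% row is correct.
- **The sample size has other support.** The second table also supports it, and its rows are all correct.
- **A misread digit is possible.** The two limits differ by one digit (4 for 6), and text extracted from a PDF can contain such errors. Every other limit in both tables agrees with the formula, so this is a reason to check the source, not a rebuttal.

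A reader might infer that the error undermines the choice of 500 patients, or that it alters how the 20% goal will be judged. The documents support neither inference, for the first two reasons above. What the reply does not remove is that a stated interval in the sample-size section is wrong, at the one proportion that the plan names as its goal for this endpoint.

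**Conclusion.** The concern holds as a wrong figure with limited consequence. At 20% and n = 500, the plan's Wald method gives (16.49%, 23.51%). As printed, the row understates the planned precision at the goal. It deserves correction because precision is the only stated statistical basis for the trial's size and because the final report will use the same interval method. If about 20% is observed in about 500 evaluable profiles, the reported limits would visibly disagree with the protocol.

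This rests on two assumptions: that the table uses the Wald formula, which the other eleven rows bear out, and that 14.49% is what the source PDF prints. The recalculation takes the table's own premise of 500 observations.

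**What to change.** Check the lower limit in the 20% row of the first Section 16.4 table against the source PDF. If it reads 14.49%, replace the row with (16.49%, 23.51%). Leave the 14.46% in the second table as it is. The cost is one number at the next amendment; no other text, sample size or analysis needs to change.

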16.5 Analysis Plan

16.51 Primary Endpoints

For the analysis of the first primary endpoint, the proportion of patients who
have an actionable genomic profile will be calculated. This is defined as the
total number of eligible patients who have an actionable genomic profile
divided by the total number of eligible patients whose genomic profile is
available for COLOMATE steering committee review.

A patient may come back to ACCRU-GI-1611 for subsequent screening (see sections 7.5, 7.5, and 7.6); therefore, a patient can contribute information to the first primary endpoint more than once.

- Our goal is to have at least 20% of patients have actionable genomic profile. The endpoint will be presented as a point estimate along with a 95% confidence interval (by Wald asymptotic confidence limit).
- For the analysis of the second primary endpoint, the proportion of patients that enroll in the companion trial recommended by the COLOMATE committee will be calculated. This is defined as the total number of eligible patients that enroll in the recommended companion trial divided by the total number of eligible patients who have an actionable genomic profile.

A patient may come back to ACCRU-GI-1611 for subsequent screening (see sections 7.4, 7.5, and 7.6); therefore a patient can contribute information to

the second primary endpoint more than once.

• Our goal is to enroll at least 75% of patients who have an actionable genomic profile. The endpoint will be presented as a point estimate along with a 95% confidence interval (by Wald asymptotic confidence limit).

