6.2 Subsequent Registrations

6.21 To register a patient, fax () a completed eligibility checklist to the Academic and Community Cancer Research United (ACCRU) Registration Office between 8 a.m. and 4:30 p.m. central time Monday through Friday.

NOTE: Patients have the option to register on COLOMATE for a maximum of 3 times or at the discretion of the Study Chair. Patients must reconsent and meet eligibility criteria in section 3 and will receive a new patient ID.

- 6.3 At the time of registration, the following will be recorded:
 - Patient has given permission to share his/her data for future research to learn about, prevent, or treat cancer or other health problems (for example: diabetes, Alzheimer's disease, or heart disease).
 - Patient has given permission for ACCRU to share his/her data to outside researchers.
- 6.4 Documentation of IRB approval must be on file with ACCRU before an

investigator may register any patients. Approvals should be uploaded through the online ACCRU Regulatory Management System (ARMS).

In addition to submitting initial IRB approval documents, ongoing IRB approval documentation must be on file with ACCRU no less than annually. Approvals should be uploaded through the online ACCRU Regulatory Management System (ARMS). If the necessary documentation is not submitted in advance of attempting patient registration, the registration will not be accepted and the patient may not be enrolled in the protocol until the situation is resolved.

Submission of annual IRB approvals to ACCRU is required until the study is closed through your IRB*.

*Please note, if the study site IRB determines that the study meets requirements for a minimal risk study, per the Revised Common Rule, any study approved after January 21, 2019, is not required to provide continuing/annual reviews.

- 6.5 Prior to accepting the registration, the registration application will verify the following:
 - IRB approval at the registering institution
 - Patient eligibility
 - Existence of a signed consent form
 - Existence of a signed authorization for use and disclosure of protected health information
- 6.6 Study-specific activities cannot begin prior to registration and must begin ≤30 days after registration.
 - NOTE: Guardant360 testing completed ≤ 60 days prior to registration will be accepted.
- 6.7 Pretreatment tests/procedures (see Section 4) must be completed within the guidelines specified on the test schedule.

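### Section 16.51 defines both primary endpoints per patient but counts returning patients repeatedly under a plain Wald interval, so it yields a per-registration proportion without assured 95% coverage of a patient proportion

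*Combined protocol and SAP*

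**What the plan says.** Section 16.51 sets the numerator of endpoint 1 as the "total number of eligible patients who have an actionable genomic profile", over eligible patients whose profile the steering committee can review. Endpoint 2 is eligible patients who enrol in the recommended trial over eligible patients with an actionable profile. The goals of 20% and 75% are also stated in patients.

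For endpoint 1 the section adds that "a patient can contribute information to the first primary endpoint more than once", and it says the same of endpoint 2. Each estimate is to be reported "along with a 95% confidence interval (by Wald asymptotic confidence limit").

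Section 6.2 allows 3 registrations, or more at the Study Chair's discretion. Returning patients reconsent, must meet the eligibility criteria again "and will receive a new patient ID". Section 7 describes who returns:

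- Section 7.42, on patients with one actionable alteration: "Patients who decline participation on the COLOMATE companion trial or do not meet eligibility criteria can subsequently register with COLOMATE". Section 7.52 says the same for two or more alterations.
- Section 7.6, on patients with no actionable alteration: "The patient can re-register with COLOMATE ≥60 days after previous registration for maximum of 3 times".

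Section 16.4 states the size in patients: "The total sample size of COLOMATE will be approximately 500 patients". Section 16.3 says: "All analyses will be done in descriptive fashion only".

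**The concern.** Two separate problems follow from counting a person more than once.

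1. **What is estimated.** Whether someone returns depends on the earlier outcome, because the section 7 routes are for people who were not actionable or did not enrol. Pooling all registrations therefore gives a ratio that generally differs from any patient proportion. A variance correction does not remove that gap.
2. **The interval.** Results from the same person are likely to be correlated. A plain Wald interval treats every registration as an independent patient, so its standard error will generally be too small.

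In a descriptive study the estimate and its interval are the whole result. A reader who sees a proportion of patients set beside a 20% or 75% goal would take it as a patient proportion, which it is not.

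**Working it through.** **Inputs from the documents.** 500 patients and 200 recommended (40%), both from section 16.4; a two-sided 95% Wald interval and the goals of 20% and 75%, from 16.51.

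**Assumed inputs.** The documents give no return rate and no correlation between a person's registrations. All such values below are assumptions.

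**The plan's own figures.** The interval is p ± 1.96·√(p(1−p)/n). At p = 0.40 and n = 500 the half-width is 1.96·√(0.24/500) = 4.29 points, giving (35.71%, 44.29%) as printed. Five of the six rows for n = 500 and all six for n = 200 reproduce. The lower limit of the 20% row is printed as 14.49% where the formula gives 16.49%, a separate slip. The tables are thus plain Wald intervals that treat 500 and 200 as independent patients.

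**Direction, endpoint 2.** Suppose each enrollee enrols once. The pooled ratio then has the same numerator as ever enrolled per person but a larger denominator, so it must lie below it. Against the first-registration proportion, the pooled ratio is a weighted average of first-time and returner enrolment, so it falls below when returners enrol less often. Section 6.2 is not limited to non-enrollees; if enrollees also return, the direction is not fixed.

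**Direction, endpoint 1.** Non-actionable patients and actionable patients who did not enrol may both return, so the direction is unknown.

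**Size, endpoint 1.** Take 500 persons, 20% actionable at first screen, and 30% return. Of the non-actionable returners, 10% become actionable; of the actionable returners, 90% repeat the result. Ever actionable is (100 + 400·0.3·0.1)/500 = 112/500 = 22.4%. Coverage is from simulation with 200,000 replicates per scenario.

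| Who returns | Pooled proportion | Coverage of 20.0% (first) | Coverage of 22.4% (ever) |
|---|---|---|---|
| (a) Non-actionable only | (100+12)/(500+120) = 18.1% | 74% | 22% |
| (b) 30% of all actionable also | (100+27+12)/(500+30+120) = 21.4% | 83% | 85% |
| (c) As (b), but 25% of actionable enrol and do not return | (100+20.25+12)/(500+22.5+120) = 20.6% | 90% | 75% |

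The true standard deviation divided by the mean Wald standard error is about 1.02 in (a), 1.16 in (b) and 1.14 in (c). With 5–10% return, coverage of the first-screen rate is 92–94%. At the plan's 40% with 30% return, (a) gives 209/590 = 35.4% (coverage 37%) and (c) gives 249.5/635 = 39.3% (89%). With 10% return, (c) gives 216.5/545 = 39.7% (93%).

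**Size, endpoint 2.** Take 200 actionable persons, of whom 60 (30.0%) enrol at first. Of the 140 non-enrollees a share returns, still actionable, and 10% of those enrol.

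- 30% return: (60+4.2)/(200+42) = 26.5%; ever enrolled 64.2/200 = 32.1%. Coverage is 74% (first) and 50% (ever).
- 10% return: (60+1.4)/214 = 28.7%; coverage 92% and 88%.
- 5% return: 29.3%; coverage 94% and 93%.
- 30% return, with 50% of returners enrolling: 81/242 = 33.5%, above first but below ever (81/200 = 40.5%).
- At the 75% goal: 150.5/205 = 73.4% with 10% return and 151.5/215 = 70.5% with 30%.

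**Correlation alone.** If 100 of 500 patients return once, regardless of outcome, with an intra-person correlation of 0.5, there are 600 records. The design effect is (400 + 100·(2 + 2·0.5))/600 = 1.167. The Wald interval at 40% is (36.08%, 43.92%) and the adjusted one (35.77%, 44.23%); coverage of the unadjusted interval is 93%.

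**A smaller point: one assay counted twice.** If the first test was completed d days after the first registration, it is still no more than 60 days old at a re-registration between day 60 and day 60+d. Section 7.11 then accepts it without a repeat. This cannot happen if the first registration used a test completed before it.

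**The case against.** The plan is open about repeat counting. It states it for both endpoints, and section 6.2 requires renewed consent, renewed eligibility and a new ID. The unit can therefore be read as the registration. That suits a protocol meant to feed companion trials while more of them open and tumour profiles change. On that reading, what is missing is a label and a variance method.

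The largest coverage losses are also mostly a mismatch of target, not a failed interval. In scenario (a) the interval covers its own per-registration mean about 94% of the time. Scenario (a) leaves out actionable non-enrollees, whom 7.42 and 7.52 let return, and (b) returns enrollees, whom section 7 does not describe. Scenario (c) is closest to section 7, and its effect is modest. For endpoint 2, if returners enrol at the same 30% as first-timers, the pooled figure is 30.0% and first-registration coverage is 95%. Applying the 90% repeat rate to the 42 returners moves 26.5% only to (60+3.78)/237.8 = 26.8%. The model also leaves out 7.6 returners who become newly actionable. Finally, a wait of at least 60 days in refractory disease, with a life-expectancy criterion of 3 months, may keep returns few.

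Most of this stands as a limit on size, and first-registration is not the only valid target. It does not remove the defect. If the unit is the registration, the definitions, both goals and the planned 500 are mislabelled, and independence still fails.

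**Conclusion.** The concern holds. As written, section 16.51 produces a per-registration ratio, labels it a patient proportion, and attaches an interval with no assured 95% coverage of any patient proportion. With few returns (about 5%) the effect is close to nil. With 30% return under the scenario nearest section 7, endpoint 1 moves by less than a point and first-screen coverage is about 89–90%. Endpoint 2 is more exposed when returners enrol less often: 26.5% against 30.0% at first and 32.1% ever. All these sizes rest on assumed return and enrolment rates. No hypothesis is tested and the goals carry no decision rule, so this should be fixed as a matter of correct labelling and valid intervals; no decision is put at risk.

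**What to change.** Amend section 16.51 as follows.

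- **Primary analysis:** one record per person, from the first registration, with the Wald interval on distinct persons. For endpoint 2 the denominator is persons actionable at first registration.
- **Supportive:** ever actionable and ever enrolled, per person.
- **Any all-registrations figure:** label it a per-registration yield and use a person-clustered variance (robust or GEE).
- **Data rules:** state that IDs are linked across a person's registrations, and that a Guardant360 result already counted under an earlier registration is not counted again.
- **Section 16.4:** state whether the planned 500 counts persons or registrations.

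The cost is wording. Enforcing the 60-day and 3-registration limits already requires recognising earlier registrations, so linkage should add little. If 500 counts registrations and 10–30% of patients return once, there are 500/1.1 = 455 to 500/1.3 = 385 persons. The width at 40%, 2·1.96·√(0.24/n), is then 9.0–9.8 points, inside the plan's 10-point target. For endpoint 2, 200/1.1 = 182 to 200/1.3 = 154 persons at 30% enrolment give 13.3–14.5 points, inside the 15-point target. The downside is that first-registration figures do not credit companion trials opened later; the ever-per-person estimates do.
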